9.1.9 Procedures for Clinical Laboratory Samples

Clinical laboratory tests that will be performed in this study are shown in Table 9.a.

All samples will be collected in accordance with acceptable laboratory procedures. The maximum volume of blood at any single visit is approximately 27 mL, and the approximate total volume of blood for the study is 322 mL.

Table 9.a Clinical Laboratory Tests

Hematology	Serum Chemistry
Red blood cells	Alanine aminotransferase
Reticulocytes	Aspartate aminotransferase
White blood cells	γ -Glutamyl transferase
Hemoglobin	Alkaline phosphatase
Hematocrit	Total bilirubin
Platelets	Total protein
White blood cells with differential (neutrophils, lymphocytes, monocytes, eosinophils, basophils)	Albumin
Erythrocyte indices (MCV, MCH, MCHC)	Creatinine
	Amylase
	Lipase
	Blood urea nitrogen
	Uric acid
	Creatine kinase
	Lactate dehydrogenase
	Total cholesterol
	Triglyceride (fasting)
	Low-density lipoprotein (LDL) cholesterol (direct measurement)
	High-density lipoprotein (HDL) cholesterol
	high-sensitivity CRP
	Potassium
	Sodium
	Calcium
	Chloride
	Phosphate
	Ferrum
Other:	
Pregnancy test (serum or urine human chorionic gonadotropin [hCG]) (female subjects of childbearing potential)	

The central laboratory (Annex 1) will perform laboratory tests listed above except for the pregnancy test. Creatinine clearance (Ccr) will be calculated by the sponsor using the Cockcroft-Gault equation.

Cockcroft-Gault equation

Male: $Ccr = \{(140 - \text{age}) \times \text{weight (kg)}\} / \{72 \times \text{serum creatinine (mg/dL)}\}$

Female: $Ccr = 0.85 \times \{(140 - \text{age}) \times \text{weight (kg)}\} / \{72 \times \text{serum creatinine (mg/dL)}\}$

If subjects experience ALT or AST $>3 \times$ ULN, follow-up laboratory tests (at a minimum, serum alkaline phosphatase, ALT, AST, total bilirubin, GGT, and INR) should be performed within a maximum of 7 days and preferably within 48-72 hours after the abnormality was noted. (Refer to Section 7.5 and Section 10.2.3)

The results of laboratory tests will be returned to the investigator or sub-investigator, who is responsible for reviewing and filing these results. The investigator will also maintain a copy of the reference ranges including their amendment for the laboratory used.

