9.3.4 Week 52 in the Treatment Period or Early Termination

All procedures scheduled for the final visit will be performed at Week 52 of the treatment period.

For subjects prematurely withdrawn from the study during the treatment period, all procedures scheduled for Week 52 will be performed within 7 days after the final dose of the study drug (reckoned from the day after the final dose) whenever possible.

For all subjects receiving study drug, the investigator or sub-investigator must complete the End of Study eCRF page.

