 - TEAEs that occur before the start of the study drug for Treatment Period II: The analysis will be performed based on the evaluation result entered in the CRF under “Pretreatment Event/Adverse Event (Period 1).”
 - TEAEs that occur after the start of SYR-472 25 mg tablet: The analysis will be performed based on the evaluation results entered in the CRFs under “Pretreatment Event/Adverse Event (Period 1)” and “Pretreatment Event/Adverse Event (Period 2 and thereafter).” If the

evaluation results differ between “Pretreatment Event/Adverse Event (Period 1)” and “Pretreatment Event/Adverse Event (Period 2 and thereafter),” the evaluation result of “Pretreatment Event/Adverse Event (Period 2 and thereafter)” will be preferentially used.

- Time of onset: In the analysis of TEAEs that occur before the start of the study drug for Treatment Period II, the time of onset will be calculated by defining the day of the start of the study drug administration as day 1. In the analysis of TEAEs that occur after the start of SYR-472 25 mg tablet, it will be calculated by defining the day of the start of SYR-472 25 mg tablet as day 1.
- Number of days from the immediate study drug administration: To be calculated by defining the day of the immediate study drug administration as Day 1. If the study drug administration and TEAE occur on the same day, the number of days from the immediate study drug administration will be defined as 1 day.
- Complications of hepatobiliary disorders: Concurrent medical conditions summarized as hepatobiliary disorders by SOC.
- MAV: An abbreviation for markedly abnormal value.
- Overall hypoglycemia: Hypoglycemia reported as “Yes” for hypoglycemic symptoms and asymptomatic hypoglycemia.
- Asymptomatic hypoglycemia: Hypoglycemia with an evaluable self-monitoring blood glucose value (i.e., non-missing and determined to be eligible based on “Handling Rules for Analysis Data”) and a measured concentration of ≤ 70 mg/dL but determined to be not accompanied by symptoms of hypoglycemia at the measurement of that blood glucose value. The presence or absence of asymptomatic hypoglycemia will be determined for each blood glucose value measured.

HANDLING OF TIME WINDOW

For each test, observation, and evaluation items, evaluable data (i.e., non-missing data and data determined to be eligible based on “Handling Rules for Analysis Data”) will be handled according to the following rules.

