The evaluable data within the acceptable window will be used. If more than one evaluable datum lies within the same acceptable window, the data whose test/observation/evaluation date is closest to the scheduled date will be used and, if there are two data equidistant to the scheduled date, the data obtained earlier will be used for efficacy endpoints and the data obtained later will be used for safety endpoints.

HbA1c

Visit	Scheduled Study Day	Acceptable Window			
		Study Day	Follow-up Day for Treatment Period I	Study Day for Treatment Period II	Follow-up Day for SYR-472 25 mg Tablet
Week -6	Study Day: -42	-49 to -29			
Week -2	Study Day: -14	-28 to -8			
Week 0	Study Day: 1	-7 to 1			
Week 2	Study Day: 15	2 to 22	~ 20	~ 1	
Week 4	Study Day: 29	23 to 42	~ 20	~ 1	
Week 8	Study Day: 57	43 to 70	~ 20	~ 1	
Week 12	Study Day: 85	71 to 98	~ 20	~ 1	
Week 16	Study Day: 113	99 to 126		2 ~	~ 20
Week 20	Study Day: 141	127 to 154		2 ~	~ 20
Week 24	Study Day: 169	155 to 182		2 ~	~ 20
Week 28	Study Day: 197	183 to 210		2 ~	~ 20
Week 32	Study Day: 225	211 to 238		2 ~	~ 20
Week 36	Study Day: 253	239 to 266		2 ~	~ 20
Week 40	Study Day: 281	267 to 294		2 ~	~ 20
Week 44	Study Day: 309	295 to 322		2 ~	~ 20
Week 48	Study Day: 337	323 to 350		2 ~	~ 20
Week 52	Study Day: 365	351 to 378		2 ~	~ 20
At the End of Treatment Period I	Follow-up Day for Treatment Period I: 7	2 ~	~ 20	~ 1	
At the End of Treatment Period II	Follow-up Day for SYR-472 25 mg Tablet: 7			2 ~ *	~ 20

*: At the end of Treatment Period II, "Study Day for Treatment Period II" will be assumed to be "Study Day for SYR-472 25 mg tablet."

Fasting blood glucose

Visit	Scheduled Study Day	Acceptable Window			
		Study Day	Follow-up Day for Treatment Period I	Study Day for Treatment Period II	Follow-up Day for SYR-472 25 mg Tablet
Week -6	Study Day: -42	-49 to -22			
Week 0	Study Day: 1	-21 to 1			
Week 2	Study Day: 15	2 to 22	~ 20	~ 1	
Week 4	Study Day: 29	23 to 42	~ 20	~ 1	

Visit	Scheduled Study Day	Acceptable Window			
		Study Day	Follow-up Day for Treatment Period I	Study Day for Treatment Period II	Follow-up Day for SYR-472 25 mg Tablet
Week 8	Study Day: 57	43 to 70	~ 20	~ 1	
Week 12	Study Day: 85	71 to 98	~ 20	~ 1	
Week 16	Study Day: 113	99 to 126		2 ~	~ 20
Week 20	Study Day: 141	127 to 154		2 ~	~ 20
Week 24	Study Day: 169	155 to 182		2 ~	~ 20
Week 28	Study Day: 197	183 to 210		2 ~	~ 20
Week 32	Study Day: 225	211 to 238		2 ~	~ 20
Week 36	Study Day: 253	239 to 266		2 ~	~ 20

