Week 44	Study Day: 309	295 to 322		2 ~	~ 20
Week 48	Study Day: 337	323 to 350		2 ~	~ 20
Week 52	Study Day: 365	351 to 378		2 ~	~ 20
Week 54	Follow-up Day for SYR-472 25 mg Tablet: 21				21 to 28
At the End of Treatment Period I	Follow-up Day for Treatment Period I: 7	2 ~	~ 20	~ 1	
At the End of Treatment Period II	Follow-up Day for SYR-472 25 mg Tablet: 7			2 ~ *	~ 20

*: At the end of Treatment Period II, "Study Day for Treatment Period II" will be assumed to be "Study Day for SYR-472 25 mg tablet."

Vital signs, laboratory test, creatinine clearance, eGFR

Visit	Scheduled Study Day	Acceptable Window			
		Study Day	Follow-up Day for Treatment Period I	Study Day for Treatment Period II	Follow-up Day for SYR-472 25 mg Tablet
Week -6	Study Day: -42	-49 to -29			
Week -2	Study Day: -14	-28 to -8			
Week 0	Study Day: 1	-7 to 1			
Week 2	Study Day: 15	2 to 22	~ 20	~ 1	
Week 4	Study Day: 29	23 to 42	~ 20	~ 1	
Week 8	Study Day: 57	43 to 70	~ 20	~ 1	
Week 12	Study Day: 85	71 to 98	~ 20	~ 1	

Visit	Scheduled Study Day	Acceptable Window			
		Study Day	Follow-up Day for Treatment Period I	Study Day for Treatment Period II	Follow-up Day for SYR-472 25 mg Tablet
Week 16	Study Day: 113	99 to 126		2 ~	~ 20
Week 20	Study Day: 141	127 to 154		2 ~	~ 20
Week 24	Study Day: 169	155 to 182		2 ~	~ 20
Week 28	Study Day: 197	183 to 210		2 ~	~ 20
Week 32	Study Day: 225	211 to 238		2 ~	~ 20
Week 36	Study Day: 253	239 to 266		2 ~	~ 20
Week 40	Study Day: 281	267 to 294		2 ~	~ 20
Week 44	Study Day: 309	295 to 322		2 ~	~ 20
Week 48	Study Day: 337	323 to 350		2 ~	~ 20
Week 52	Study Day: 365	351 to 378		2 ~	~ 20
Week 54	Follow-up Day for SYR-472 25 mg Tablet: 21				21 to 28

12-lead ECG

Visit	Scheduled Study Day	Acceptable Window			
		Study Day	Follow-up Day for Treatment Period I	Study Day for Treatment Period II	Follow-up Day for SYR-472 25 mg Tablet
Week -6	Study Day: -42	-49 to -22			
Week 0	Study Day: 1	-21 to 1			
Week 4	Study Day: 29	2 to 56	~ 20	~ 1	
Week 12	Study Day: 85	57 to 98	~ 20	~ 1	
Week 24	Study Day: 169	99 to 210		2 ~	~ 20
Week 36	Study Day: 253	211 to 308		2 ~	~ 20
Week 52	Study Day: 365	309 to 378		2 ~	~ 20
Week 54	Follow-up Day for SYR-472 25 mg Tablet: 21				21 to 28

Plasma concentration of SYR-472Z

Visit	Scheduled Study Day	Acceptable Window			
		Study Day	Follow-up Day for Treatment Period I	Study Day for Treatment Period II	Follow-up Day for SYR-472 25 mg Tablet
Week 4	Study Day: 29	23 to 42	~ 20	~ 1	
Week 12	Study Day: 85	71 to 98	~ 20	~ 1	

OTHER HANDLING

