3.3 Clinical Laboratory Evaluations and Other Safety Endpoints

3.3.1 Clinical Laboratory Evaluations

3.3.1.1 Hematology and Serum Chemistry

Analysis set:	Safety analysis set		
Analysis variables:	Hematology		
	Red blood cells	Reticulocytes	White blood cells
	Hemoglobin	Hematocrit	Platelets
	Neutrophils	Lymphocytes	Monocytes
	Eosinophils	Basophils	MCV
	MCH	MCHC	
	Serum chemistry		
	ALT	AST	
	γ-GTP	ALP	
	Total bilirubin	Total protein	
	Albumin	Creatinine	
	Amylase	Lipase	
	Blood urea nitrogen	Uric acid	
	Creatine kinase	LDH	
	Total cholesterol	Triglyceride	
	LDL cholesterol	HDL cholesterol	
	High-sensitivity CRP	K	
	Na	Ca	
	Cl	P	
	Fe	Creatinine clearance	
Categories:	Adjudication results based on the normal reference ranges [Low, Normal, High]		
Visits:	Weeks -6, -2, 0, 2, 4, 8, 12, 16, 20, 24, 28, 32, 36, 40, 44, 48, 52, and		

Analysis methodology: The following analysis will be performed for the above analysis variables except for high-sensitivity CRP and creatinine clearance by treatment group. The following analyses of (1) to (2) will be performed for high-sensitivity CRP and creatinine clearance by treatment group.

When the analysis of MAV is performed, if both “upper” and “lower” criteria in the MAV Criteria are applicable to the same test item, the analysis will be performed for each criterion separately. See Appendix 2 of this SAP for the definitions of test items subject to this analysis and the MAV Criteria.

- (1) Summary statistics for each visit and summary statistics for change from Week 0 at each visit after Treatment Period I
- (2) Case plots
- (3) Shift tables showing adjudication results based on normal reference range at Week 0 and each visit after Treatment Period I
- (4) Frequency distributions for MAV before the start of the study drug administration for Treatment Period II and after the start of SYR-472 25 mg tablet

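### The safety window rule can leave unscheduled and some early-termination laboratory and ECG values out of the by-visit tables, and the SAP does not say which values the MAV counts use

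*SAP*

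**What the plan says.** The SAP section on handling of time windows opens with a rule of general scope: "For each test, observation, and evaluation items, evaluable data" are handled by the rules that follow. Only values inside an acceptable window are used. "If more than one evaluable datum lies within the same acceptable window, the data whose test/observation/evaluation date is closest to the scheduled date" is the one taken. For an exact tie in distance, "the data obtained later will be used for safety endpoints". There is no worst-value rule.

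The window tables then differ by type of endpoint. HbA1c, fasting glucose, glycoalbumin, C-peptide, glucagon/DPP-4 activity and weight each have a row for the end of Period I and one headed "At the End of Treatment Period II". The table headed "Vital signs, laboratory test, creatinine clearance, eGFR" and the 12-lead ECG table have neither. Their last row, Week 54, is defined only by Follow-up Day for the SYR-472 25 mg tablet, Days 21 to 28.

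In SAP 3.3.1.1 and 3.3.2.2 the summary statistics and shift tables are by visit. The MAV analysis is by period: "Frequency distributions for MAV before the start of the study drug administration for Treatment Period II", and likewise after the start of the SYR-472 25 mg tablet. Neither section says whether it uses windowed values or all evaluable values. Both refer to Appendix 2 for the definitions, and that appendix is not in the supplied text.

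The protocol generates values off the visit schedule. For subjects withdrawn during treatment, section 9.3.4 says that "all procedures scheduled for Week 52 will be performed within 7 days after the final dose of the study drug", whenever possible. After ALT or AST above 3 times the upper limit, section 9.1.9 says repeat tests "should be performed within a maximum of 7 days and preferably within 48-72 hours after the abnormality was noted".

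**The concern.** Laboratory values and ECG are secondary safety endpoints, and QT prolongation is an adverse event of special interest. Values taken off schedule are often taken because something looked wrong. Under a nearest-to-schedule rule, such a value loses to an on-time value from the same window, however abnormal it is. The SAP guards against this for an early-termination HbA1c but not for an early-termination ALT or QTcF.

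At stake is whether the by-visit safety tables show the last on-treatment value and unscheduled extremes. If the same rule also governs the MAV counts, the tables meant to catch extremes would be incomplete too. The missing follow-up row affects only one arm.

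**Working it through.** The plan states no figure on this point, so the check is a count of days against the SAP windows.

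**Inputs and assumptions.** The windows are those of the SAP laboratory/vital-sign and ECG tables. Early-termination tests fall within 7 days of the last dose, inside the Follow-up Day limit of 20, so that limit excludes none of them. Assumptions: earlier visits took place exactly on the scheduled day, Period II starts on Study Day 85, and there is one termination value, equally likely on each of Study Days 2 to 364 (363 days).

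**Rule applied.** A termination value before the scheduled day is the only value in its window and is kept. One after the scheduled day, in the same window, is displaced, because the on-time value is at distance 0.

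| Laboratory window (scheduled day) | Days after scheduled day | Unused |
|---|---|---|
| Week 2: 2–22 (15) | 16–22 | 7 |
| Week 4: 23–42 (29) | 30–42 | 13 |
| Week 8: 43–70 (57) | 58–70 | 13 |
| Week 12: 71–98 (85) | 86–98 | 13, in no window |
| Weeks 16–48: nine windows | 13 each | 117 |
| Week 52: 351–378 (365) | none by Day 364 | 0 |

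Displaced: 7 + 13 + 13 + 117 = 150. In no window: 13. Total 163; 163/363 = 45%. Kept: 200/363 = 55%.

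| ECG window (scheduled day) | Days after scheduled day | Unused |
|---|---|---|
| Week 4: 2–56 (29) | 30–56 | 27 |
| Week 12: 57–98 (85) | 86–98 | 13, in no window |
| Week 24: 99–210 (169) | 170–210 | 41 |
| Week 36: 211–308 (253) | 254–308 | 55 |
| Week 52: 309–378 (365) | none by Day 364 | 0 |

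Displaced: 27 + 41 + 55 = 123. In no window: 13. Total 136; 136/363 = 37%. Kept: 227/363 = 63%.

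**The 13 days in no window.** The Week 12 row requires Period II Day 1 or earlier, and the Week 16 row requires Study Day 99 or later. With Period II starting on Day 85, Days 86 to 98 satisfy neither: 98 − 85 = 13 days. These values do not lose to a closer one; they have nowhere to go.

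**Subjects who never enter Period II (Days 2–98, 97 days).** The Week 12 window then runs to Day 98. Laboratory: 7 + 13 + 13 + 13 = 46 displaced, 51 kept. ECG: 27 + 13 = 40 displaced, 57 kept.

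**Liver retests.** A retest 2 to 7 days after an on-time visit lies in the same Study Day window at all 14 post-baseline visits (the tightest is Week 2: 15 + 7 = 22, the last day of that window), so it is never selected. After Week 12, once Period II has begun, it has no window.

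**Placebo follow-up.** Protocol 9.3.5 sets the end-of-follow-up tests at the 21st day after the last dose. The Period I windows stop at Follow-up Day 20. The Week 54 row needs a last SYR-472 25 mg tablet, which a placebo subject who stops in Period I never took. A SYR-472 subject who stops in Period I does have that row.

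**The case against.** A reader might infer that early-termination values as a class, including those that led to stopping, drop out of the MAV tables, so that MAV frequencies are biased downward. The documents do not support that.

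- The MAV tables are by period, not by visit. Their source values are not stated, and both Appendix 2 and the separate handling rules for analysis data are outside the supplied text. The general rule read literally would restrict them, and nothing supplied exempts them. By contrast, the SAP's definition of asymptomatic hypoglycemia says expressly that every measured glucose value is judged. This remains an ambiguity, not a demonstrated loss.
- More than half of termination days keep the value (55% laboratory, 63% ECG). An abnormal value found at an on-time scheduled visit is kept even if it led to stopping; what is passed over is the later value.
- The percentages are shares of calendar days, not of subjects or abnormal values. Dosing is weekly and visit procedures precede dosing, so a subject stopped at an on-time visit may have that visit serve as the termination visit, and its value is kept.
- Clinically significant changes are recorded as adverse events. The SAP tabulates events leading to discontinuation and QT-related and renal events, and it plans case plots. This capture is partial: Protocol 10.1.3 makes a laboratory or ECG change an adverse event only on a judgement of clinical significance, and accompanying abnormal values are not recorded separately once a diagnosis is.
- Laboratory shift tables have only low, normal and high categories. A retest that moves from high to higher would not change the category, so the loss there matters mainly when the scheduled value was in a different category.
- One value per visit is a reasonable convention for by-visit tables. The missing follow-up row concerns post-treatment data from placebo subjects who stop in Period I, and their number is unknown.

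These points limit the size of the problem. They do not answer the absence of end-of-treatment rows, the two gaps, or the silence on MAV source data.

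**Conclusion.** The point holds in limited form. The selection rule and the missing rows are in the SAP text, so the by-visit laboratory and ECG summaries and shift tables can omit unscheduled values and some early-termination values; vital-sign summaries share the same windows. Two gaps are certain on the wording: Period II Day 2 to Study Day 98, and end of follow-up for placebo subjects who stop in Period I. The effect on MAV counts is open until Appendix 2 is checked.

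The 45% and 37% illustrate the mechanism under on-time visits, a uniform termination day and Period II starting on Day 85. They are not forecasts of lost data. The case for changing the plan is that the correction is cheap and the present rule can hide extreme safety values.

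**What to change.** 1. State in SAP 3.3.1.1(4) and 3.3.2.2(3) that MAV counts use all evaluable post-baseline values in the period, including unscheduled and early-termination values, unless Appendix 2 already says so. No value is then lost from these counts through windowing.
2. Add end-of-Period-I and end-of-Period-II rows to the laboratory and ECG windows and shift tables, as for efficacy, and to the vital-sign summaries. Add a worst post-baseline category to the laboratory and ECG shift tables, because an end-of-treatment row still keeps only one value and would miss an unscheduled peak.
3. Assign values from Period II Day 2 to Study Day 98 to a window.
4. For placebo subjects who stop in Period I, define a follow-up row by Follow-up Day for Treatment Period I.

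The cost is SAP wording and table programming; no new data are needed. MAV frequencies may come out slightly higher, and there will be a few extra table rows.

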1 STUDY SUBJECTS, DEMOGRAPHICS, AND OTHER BASELINE CHARACTERISTICS

1.1 Disposition of Subjects

1.1.1 Study Information

Analysis set: All subjects who signed the informed consent form

Analysis variables: Date first subject signed the informed consent form
Date of last visit or contact, whichever comes later
MedDRA version
WHO Drug version
SAS version used for creating the datasets

Analysis methodology: The following analysis will be performed for the above analysis variables.
(1) Display of the analysis variables

1.1.2 Disposition of All Subjects Who Were Not Randomized

Analysis set: All subjects who were not randomized

Analysis variables: Categories in brackets [] (hereinafter the same)
Age (years) [Min≤ - <65, 65≤ - ≤Max]
Sex [Male, Female]

Analysis methodology: The following analysis will be performed for the above analysis variables.
(1) Frequency distributions for categorical variables and summary statistics for continuous variables

1.1.3 Subject Eligibility

Analysis set: All subjects who signed the informed consent form

Analysis variables: Eligibility for randomization [Eligible, Not eligible]
Reason for not being randomized [Pretreatment event/Adverse event, Significant protocol deviation, Lost to follow-up, Voluntary withdrawal, Study termination, Pregnancy, Did not meet inclusion criteria or did meet exclusion criteria, Other]

Analysis methodology: The following analysis will be performed for the above analysis variables.
When calculating percentages for the reasons for not being

randomized, the number of subjects who were not randomized will be used as the denominator.

(1) Frequency distribution

1.1.4 Number of Subjects Who Were Randomized by Site

Analysis set:	All subjects who were randomized
Analysis variables:	Eligibility for randomization
Stratum:	Study site
	[Site numbers will be used as categories]

Analysis methodology: The following analysis will be performed for the above analysis variables for each stratum by each treatment group and in the consolidated treatment groups.

(1) Frequency distribution

1.1.5 Disposition of Subjects

1.1.5.1 Disposition of Subjects in Treatment Period I

Analysis set:	All subjects who were randomized
Analysis variables:	Study drug administration status
	Reason for not being treated
	[Not treated] [Pretreatment event/Adverse event, Significant protocol deviation, Lost to follow-up, Voluntary withdrawal, Study termination, Pregnancy, Lack of efficacy, Other]
	Study drug administration status for Treatment Period II
	Reason for not being treated
	[Treated, Not treated] [Pretreatment event/Adverse event, Significant protocol deviation, Lost to follow-up, Voluntary withdrawal, Study termination, Pregnancy, Lack of efficacy, Other]

Analysis methodology: The following analysis will be performed for the above analysis variables by each treatment group and in the consolidated treatment groups. When calculating percentages of the reasons for not being treated, the number of subjects who did not receive with the study

drug will be used as the denominator.

(1) Frequency distribution

